9.1.7 Documentation of Concomitant Medications

Concomitant medication is any drug given in addition to the study medication. These may be prescribed by a physician or obtained by the subject over the counter. Concomitant medication is not provided by Takeda. At each study visit, subjects will be asked whether they have taken any medication other than the study medication (used from signing of informed consent through the end of the study), and all medication including vitamin supplements, over-the-counter medications, and oral herbal preparations, must be recorded in the (e)CRF.

9.1.8 Documentation of Concurrent Medical Conditions

Concurrent medical conditions are those significant ongoing conditions or diseases that are present at signing of informed consent. This includes clinically significant laboratory, electrocardiogram (ECG), or physical examination abnormalities noted at screening examination. The condition (ie, diagnosis) should be described.

9.1.9 Procedures for Clinical Laboratory Samples

All samples will be collected in accordance with acceptable laboratory procedures. The maximum volume of blood at any single visit is approximately 10 mL, and the approximate total volume of blood for the study is 20 mL.

Table 9.a Clinical Laboratory Tests

Hematology	Serum Chemistry	Urinalysis
Red blood cells (RBC)	Alanine aminotransferase	pH
White blood cells (WBC)	Albumin	Protein
Hemoglobin	Alkaline phosphatase	
	Aspartate aminotransferase	
Other:		
Urine		
hCG for pregnancy (only for female subjects of childbearing potential)		

The local laboratory will perform laboratory tests for hematology, serum chemistries, and urinalysis. The results of laboratory tests will be returned to the investigator, who is responsible for reviewing and filing these results.

If subjects experience ALT or AST $>3 \times$ ULN, follow-up laboratory tests (at a minimum, serum alkaline phosphatase, ALT, AST, total bilirubin, GGT) should be performed within a maximum of 7 days and preferably within 48-72 hours after the abnormality was noted.

(Please refer to Section 7.5 for discontinuation criteria, and Section 10.2.3 for the appropriate guidance on Reporting of Abnormal Liver Function Tests in relation to ALT or AST $>3 \times$ ULN in conjunction with total bilirubin $>2 \times$ ULN.)

If the ALT or AST remains elevated $>3 \times$ ULN on these 2 consecutive occasions the investigator must contact the Medical Monitor for consideration of additional testing, close monitoring, possible discontinuation of study medication, discussion of the relevant subject details and possible alternative etiologies. The abnormality should be recorded as an AE (please refer to Section 10.2.3 Reporting of Abnormal Liver Function Tests for reporting requirements).

The investigator or designee is responsible for transcribing or attaching laboratory results to the (e)CRF. The investigator will maintain a copy of the laboratory accreditation and the reference ranges for the laboratory used.

9.1.10 Contraception and Pregnancy Avoidance Procedure

From signing of informed consent, throughout the duration of the study, and for 3 weeks after last dose of study medication, nonsterilized** male subjects who are sexually active with a female partner of childbearing potential* must use barrier contraception (eg, condom with spermicidal cream or jelly). In addition, they must be advised not to donate sperm during this period.

From signing of informed consent (for oral contraceptives – for at least 90 days prior to Screening), throughout the duration of the study, and for 3 weeks after last dose of study medication, female subjects of childbearing potential* who are sexually active with a nonsterilized male partner** must use adequate contraception. In addition they must be advised not to donate ova during this period.

*Females NOT of childbearing potential are defined as those who have been surgically sterilized (hysterectomy, bilateral oophorectomy or tubal ligation) or who are postmenopausal (eg, defined as at least 1 year since last regular menses with an FSH >40 IU/L or at least 2 years since last regular

menses, confirmed before any study medication is implemented).

**Sterilized males should be at least 1 year postvasectomy and have confirmed that they have obtained documentation of the absence of sperm in the ejaculate.

An acceptable method of contraception is defined as one that has no higher than a 1% failure rate. In this study the acceptable methods of contraception are:

Barrier methods (each time the subject has intercourse):

- Male condom PLUS spermicide.
- Cap (plus spermicidal cream or jelly) PLUS male condom and spermicide.
- Diaphragm (plus spermicidal cream or jelly) PLUS male condom and spermicide.

Intrauterine devices (IUDs):

- Copper T PLUS condom or spermicide.
- #Progesterone T PLUS condom or spermicide.

Hormonal contraceptives*:**

- Implants.
- Hormone shot/injection.
- Combined pill.
- Minipill.
- Patch.
- Vaginal ring PLUS male condom and spermicide.

***In case oral contraceptives are used for less than 90 days before screening barrier methods should be used in addition to oral contraceptives.

Subjects will be provided with information on acceptable methods of contraception as part of the subject informed consent process and will be asked to sign a consent form stating that they understand the requirements for avoidance of pregnancy, donation of ova during the course of the study.

During the course of the study, regular urine human chorionic gonadotropin (hCG) pregnancy tests will be performed only for women of childbearing potential and subjects will receive continued guidance with respect to the avoidance of pregnancy as part of the study procedures ([Appendix A](#)).

9.1.11 Pregnancy

If any subject is found to be pregnant during the study she should be withdrawn and any sponsor-supplied drug should be immediately discontinued. In addition, any pregnancies in the partner of a male subject during the study or for 12 weeks after the last dose, should also be recorded following authorization from the subject's partner.

If the pregnancy occurs during administration of active study medication, eg, after Visit 1 or within 21 days of the last dose of active study medication, the pregnancy should be reported immediately, using a pregnancy notification form, to the contact listed in Section 1.0.

Should the pregnancy occur during or after administration of blinded drug, the investigator must inform the subject of their right to receive treatment information. If the subject chooses to receive unblinded treatment information, the individual blind should be broken by the investigator. Subjects randomized to placebo need not be followed.

If the female subject agrees to the primary care physician being informed, the investigator should notify the primary care physician that the subject was participating in a clinical study at the time she

became pregnant and provide details of treatment the subject received (blinded or unblinded, as applicable).

All pregnancies in subjects on active study drug including comparator will be followed up to final outcome, using the pregnancy form. Pregnancies will remain blinded to the study team. The outcome, including any premature termination, must be reported to the sponsor. An evaluation after the birth of the child will also be conducted.

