7.2 Exclusion Criteria

Any subject who meets any of the following criteria will not qualify for entry into the study:

1. The subject has muscular pain secondary to acute trauma or fractures (e.g., due to osteoporosis). Such conditions could have been ruled out based on medical history, x-ray, or physical examination.
2. The subject suffers from muscle spasms/pain related to polymyalgia rheumatica or ankylosing spondylitis (Bekhterev's disease). Such conditions could have been ruled out based on medical history, x-ray, or physical examination;
3. The subject has received any investigational compound within 30 days prior to Screening.
4. If female, the subject is pregnant or lactating or intending to become pregnant before, during, or within 1 month after participating in this study; or intending to donate ova during such time period.

5. The subject has a history of drug abuse or recent (within the last 12 months) history of excessive alcohol consumption defined as >2 drinks/day (>3 oz of 80 proof alcohol or equivalent).
6. Patients with mild, moderate, severe liver impairment.
7. The subject is an immediate family member, study site employee, or is in a dependent relationship with a study site employee who is involved in conduct of this study (eg, spouse, parent, child, sibling) or may consent under duress.
8. The subject takes any concomitant medication including over-the-counter and herbal products for muscle spasms. If a subject is taking such medications, the medications has to be discontinued before starting the study.
9. The subject takes or took within last 14 days medications, such as:
 - a. selective serotonin reuptake inhibitors (SSRIs);
 - b. serotonin norepinephrine reuptake inhibitors (SNRIs);
 - c. tricyclic antidepressants (TCAs);
 - d. MAO inhibitors;
 - e. tramadol;
 - f. bupropion;
 - g. meperidine;
 - h. verapamil; topical anti-inflammatory medications, including patches
 - i. paracetamol
 - j. opioid analgesics
10. The subject takes or took within last 3 days medications, such as:
 - a. non-steroid anti-inflammatory drugs (NSAIDs);
 - b. Intramuscular vitamin injections containing anaesthetics (such as vitamin Milgamma).
11. The subject has a history or clinical manifestations of significant medical condition, such as:
 - a. hyperthyroidism;
 - b. acute recovery phase of myocardial infarction;
 - c. arrhythmias, heart block or conduction disturbances;
 - d. congestive heart failure;
 - e. angle-closure glaucoma;

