Assessment of the subject’s answers will be made for the Day 3, 7 and 15.

- **The subject-rated intensity of local pain:**

Subjects will be asked to assess on a daily basis (in the daily diary) their intensity of local pain due to the muscle spasm (in either the lower back or cervical spine) using the following digital rating scale. It is necessary to mark the intensity of pain by circling a one of the 11 points from 0 "No Pain" to 10 "Severe Pain" with an intermediate value of 5 - "Moderate Pain".

Facial pain scale is presented to help the patient to identify the primary area of the intensity of the pain experienced:

Assessment of the subject’s answers will be made for the Day 3, 7 and 15.

- **Subject-Rated Clinical Global Impression:**

[figure not shown]
Subjects will be asked to assess on a daily basis (in the daily diary) their clinical global impression of change compared to Baseline, based on rating on medication helpfulness, relief from local pain, restriction in activities of daily living, restriction of movement.

Assessment of the subject’s answers will be made for the Day 3, 7 and 15.

Company Confidential Information

Company Confidential Information

Company Confidential Information

- Hematology, blood chemistry, urinalysis, urine pregnancy testing (if applicable), vital signs, physical examinations, and ECGs will be performed at Screening and study termination. Vital signs will be recorded at each clinic visit. Monitoring and recording of AEs will be performed during each clinic visit and continued for 3 weeks after the last dose of study drug.

Other assessments:

- **Presence of muscle spasm**

The physician was asked to evaluate the presence of muscle spasm by palpation (increased consistency of a muscle or group of muscles) using the following 5-point rating scale at each visit:

“1 = none” (no muscle spasm present)

“2 = mild” (the muscle is somewhat harder than usual)

“3 = moderate” (muscles are hard and borders of increased consistency can be determined by palpation)

“4 = moderately severe” (muscles are very hard and borders are sharply defined by palpation)

“5 = severe” (board-like hardness of the muscles)

- **Presence of local pain**

The physician was asked to assess the presence of local pain due to muscle spasm by palpation (tenderness on palpation) using the following 5-point rating scale at each visit:

“1 = none” (no pain)

“2 = mild” (complaint of local discomfort on palpation)

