9.3.5 Follow-up call

Follow-up telephone calls will be used to monitor AEs for 3 weeks after the last dose of study drug.

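### Section 9.1.11 sets pregnancy-reporting rules that the contact schedule and the blinding do not support: a 12-week partner window against contact to 3 weeks, and reporting and follow-up worded by treatment arm

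*Protocol*

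**What the plan says.** Two parts of the protocol meet here: the pregnancy rules in section 9.1.11 and the contact schedule.

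**Windows.** For partners of male subjects, section 9.1.11 states that "any pregnancies in the partner of a male subject during the study or for 12 weeks after the last dose, should also be recorded", once the partner has given authorization. For pregnancies under study medication the period is shorter: "within 21 days of the last dose of active study medication, the pregnancy should be reported immediately". Contact after treatment is described in one sentence of section 9.3.5: "Follow-up telephone calls will be used to monitor AEs for 3 weeks after the last dose of study drug". Sections 6.1 (21-day follow-up period) and 10.2.1.1 (adverse event collection) end at the same time, as does the contraception period in section 9.1.10. Section 9.1.6 gives the timing of pregnancy tests: "urine pregnancy testing (if applicable), vital signs, physical examinations, and ECGs will be performed at Screening and study termination".

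**Who is reported and followed.** The trigger in "within 21 days of the last dose of active study medication, the pregnancy should be reported immediately" is worded for active medication. After a sentence on unblinding at the subject's choice, the section adds: "Subjects randomized to placebo need not be followed". Two paragraphs later it says: "All pregnancies in subjects on active study drug including comparator will be followed up to final outcome", and then: "Pregnancies will remain blinded to the study team".

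**The concern.** A duty to record needs a way for the information to reach the site. The partner window runs well past the last planned contact, and the protocol names no means of learning of a partner pregnancy in that stretch. A smaller gap of the same kind exists for female subjects between the last test and the end of their 21-day reporting period.

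A reporting rule in a double-blind trial also has to be usable by someone who does not know the allocation. Section 9.1.11 makes both the trigger and the follow-up depend on the arm, and two of its sentences point in opposite directions for placebo.

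What is at stake is the completeness and consistency of a safety record. Appendix E states that no controlled studies have been done in pregnant women, so a pregnancy near dosing is worth recording properly. Efficacy conclusions are not at stake.

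**Working it through.** **Inputs.** Screening up to 5 days, treatment 14 days, follow-up 21 days, total participation about 35 to 40 days (section 6.1). Last dose on the evening of Day 14 (section 9.3.2). Final visit with the last pregnancy test on Day 15 (section 9.3.4). Partner window 12 weeks after the last dose; reporting window 21 days after the last dose (section 9.1.11). Follow-up telephone contact to 3 weeks after the last dose (section 9.3.5).

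**The plan's own figure.** 14 + 21 = 35 days and 5 + 14 + 21 = 40 days. This reproduces the stated 35 to 40 days, so the schedule is consistent and participation ends about study Day 14 + 21 = 35.

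**Partner window against contact.**
- Window: 12 × 7 = 84 days after the last dose, to about study Day 14 + 84 = 98.
- Planned contact: 21 days after the last dose, to about study Day 35.
- Without planned contact: 84 − 21 = 63 days, or 9 weeks.

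No other text covers those 63 days. Appendix C, item 26, deals with a partner's pregnancy found during the study. Section 10.2.2 deals with events reported spontaneously after the collection period, but only serious ones considered related to participation.

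**Female subjects.** For a subject who completes treatment, the reporting window closes on about Day 14 + 21 = 35 and the last test is on Day 15. Section 9.3.3 lists no test at the Day 3 and Day 7 visits. Section 9.1.10 speaks of regular tests and refers to Appendix A, of which only part is legible here, but no legible text places a test after Day 15. From then on, capture depends on what the follow-up call happens to elicit or on what the subject volunteers.

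**The arm-based sentences, side by side.**

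| Sentence in section 9.1.11 | What it needs | Effect for a placebo subject |
|---|---|---|
| Immediate reporting, tied to active medication | Allocation, if read literally | Outside the trigger |
| Placebo subjects need not be followed | Allocation | Exempt |
| Active drug including comparator followed to outcome | Allocation, unless comparator means placebo | Included, since placebo is the only comparator (section 8.1.3) |
| Pregnancies stay blinded to the study team | No allocation | Not distinguishable |

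After a pregnancy, section 9.1.11 breaks the blind only if the subject chooses to know. If she declines, the site has no allocation by which to apply the first two rows. If she accepts and was on placebo, the second and third rows give different instructions.

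**The case against.** The case on the other side is substantial, and much of it stands.

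- **A passive window is not a contradiction.** Section 9.1.11 asks for partner pregnancies to be recorded; it does not promise active contact for 12 weeks. Spontaneous reports are possible, and the consent form and the pregnancy notification form, which are not at hand, may ask subjects to report. A reader might infer that exposed pregnancies will be missed. The documents support only that some may be.
- **Calendar days are not exposed pregnancies.** A reader might take 63/84 = 75% as the share of exposed pregnancies lost. It is not. With the 32-hour half-life in Appendix E, 21 days is 504 hours, and 504/32 is about 16 half-lives, so conceptions in the uncovered stretch follow negligible residual drug. The relevant cases are conceptions near dosing that are recognised only after week 3, and the documents give no figure for these. For female subjects, too, a count of days after the last test says nothing about the chance of detection, because a pregnancy can be reported without a site test.
- **A blinded site may simply treat every case alike.** The placebo exemption follows the sentence on unblinding and can be read as applying once the arm is known. It is permissive, and the trigger gives the time after Visit 1 as an example, which a site could apply to any dosed subject. So the wording does not by itself lose cases. What remains is that sites may read it differently, and that the placebo exemption conflicts with the inclusion of the comparator.
- **Losing a concurrent control.** A reader might object that following only the active arm removes the comparison. The protocol plans no comparison of pregnancies, so nothing is removed.
- **The eligibility criterion.** Section 7.2 excludes women "intending to become pregnant before, during, or within 1 month after participating in this study", while contraception ends 3 weeks after the last dose. This may look like another conflict. One is a test of intent at entry and the other a duty during the study, and they can differ in length.

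**Conclusion.** The point holds as a minor safety-reporting matter with two parts. First, the partner recording duty outlasts all planned contact by 63 of its 84 days, and the reporting period for female subjects runs on after the last test with no pregnancy question described for the call, so some pregnancies may go unrecorded. Second, reporting and follow-up are worded by treatment arm in a trial where the site does not know the arm by default, and the sentences on placebo and on the comparator disagree.

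This assumes that no duty to report later is set out in the consent or notification forms, and that the unreadable part of Appendix A holds no test after Day 15. The number of pregnancies should be small: 180 subjects, 14 days of dosing, required contraception and exclusion of pregnant women. The primary analysis, sample size and error rate do not change. Which period or follow-up rule is right is for the sponsor to decide.

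**What to change.** 1. **Section 9.3.5:** add a question on pregnancy, for the subject and for the partner, to the follow-up call already planned.
2. **Section 9.1.11:** reconcile the trigger, the placebo exemption, the comparator sentence and the blinding statement, so that a site can apply reporting and follow-up without knowing the allocation.
3. **Sections 6.1, 9.1.10, 9.1.11 and 9.3.5, and Appendix C, item 26:** reconcile the 12-week partner window with the planned contact. The sponsor should choose and justify the period and state how information is to reach the site until it ends.

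The cost is protocol wording and one question in an existing call. Should the sponsor keep a window longer than the present contact, it would also have to provide a means of collection for that time. No statistical figure in the plan is affected.

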9.1.12 ECG Procedure

A standard 12-lead ECG will be recorded at Screening and Study termination. The investigator (or a qualified observer at the investigational site) will interpret the ECG using 1 of the following categories: within normal limits, abnormal but not clinically significant, or abnormal and clinically significant.

9.1.13 Documentation of Screen Failure

Investigators must account for all subjects who sign informed consent.

If the subject is found to be not eligible at this visit, the investigator should complete the (e)CRF. The data to be collected in CRF for Screen Failures as a minimum: Subject Number and Initials, Date of Informed consent, Demographics data, Inclusion/Exclusion criteria, PTEs/SAEs, Date of Screen failure.

The primary reason for screen failure is recorded in the (e)CRF using the following categories:

- PTE/AE.
- Did not meet inclusion criteria or did meet exclusion criteria.
- Significant protocol deviation.
- Lost to follow-up.
- Voluntary withdrawal (specify reason).
- Study termination.
- Other (specify reason).

Subject numbers assigned to subjects who fail screening should not be reused.

9.1.14 Documentation of Randomization

Only subjects who meet all of the inclusion criteria and none of the exclusion criteria are eligible for randomization into the treatment phase.

If the subject is found to be not eligible for randomization, the investigator should record the primary reason for failure on the applicable (e)CRF.

9.2 Monitoring Subject Treatment Compliance

Subjects will be required to bring the dispensed study medication bottle to each site visit.

Treatment compliance will be checked by Investigator at Visits 2, and 3. In case of compliance deviation all subjects should be reinstructed about the dosing requirement during study contacts. The

authorized study personnel conducting the re-education must document the process in the subject source records.

Treatment compliance for entire treatment period will be calculated at V4 using the formula:

Compliance in % = (# tablets taken during treatment period / # tablets to be taken during treatment period)*100

Any noncompliance from the administered dose must be documented as protocol deviation.

If treatment compliance is outside of 70% - 130% ranges for the entire treatment period, it should be reported as significant protocol deviation.

